## **6. Analysis Sets**

The following subsections define the analysis sets for this study.

### **6.1 Full Analysis Set**

The Full Analysis Set (FAS) includes all randomized subjects. Subjects will be analyzed according to their randomized treatment, regardless of the treatment received.

Tabulations of demographic and baseline characteristics, disposition, important protocol deviations (IPD) and protocol deviations related to COVID-19 control measures will utilize this analysis set.

### **6.2 Safety Analysis Set**

The safety analysis set will consist of all randomized subjects who received at least one dose of AMG 334 during ITP. Subjects will be analyzed according to the randomized treatment unless a subject has received the incorrect dose during the entire ITP. Analyses for safety endpoints **and summary of IP administration in ITP and for entire study duration** will utilize this analysis set.

### **6.3 Pharmacokinetic/Pharmacodynamic Analyses Set(s)**

The Pharmacokinetic (PK) analysis set will contain all randomized subjects who receive at least one dose of AMG 334 and have at least one PK concentration result.

Pharmacodynamic (PD) analysis set is not applicable for this study.

### **6.4 Interim Analyses Set(s)**

The interim analysis set will be defined separately for each interim analysis. For the first interim analysis, the analysis set will include a subset of the safety analysis set consisting of at least 6 adolescents (12 to < 18 years of age) who have completed study Week 8 assessments and all available data collected for all subjects up to and including the corresponding data cutoff date. For the second interim analysis, the analysis set will include a subset of the safety analysis set consisting of at least **8** children (6 to < 12 years of age) who have completed study Week 12 assessments and will include all available data collected for all children up to and including the corresponding data cutoff date.

## 6.5 Extension Analysis Set

The Extension Analysis Set will consist of all adolescent subjects receiving at least one dose of AMG 334 in the OEP. This analysis set will be used when summarizing data collected during the OEP.

## 7. Planned Analyses

There are two planned interim analyses, one primary analysis, and one final safety analysis.

### 7.1 Interim Analysis and Early Stopping Guidelines

There are 2 interim analyses of PK and safety planned for this study. The first interim analysis will occur when at least 6 adolescents (12 to < 18 years of age) have completed study Week 8 assessments. The second interim analysis will occur when at least 8 children (6 to < 12 years of age) have completed study Week 12 assessments. All data collected up to and including the corresponding data cutoff date will be available but only AEs, vital sign data and laboratory data will be summarized by GBS group, and PK data will be analyzed by Clinical Pharmacology Modeling and Simulation (CPMS) group. The purpose of the first and second interim analyses is to inform the selection of AMG 334 doses to be evaluated in the AMG 334 Phase 3 pediatric studies.

Results from the interim analyses will be presented to the independent Data Monitoring Committee (DMC) responsible for reviewing and making recommendations regarding the AMG 334 Phase 3 pediatric studies. The DMC will not review individual patient level data from this study or make recommendations regarding this study.

Impact of any changes in data during any analysis as compared to previous analysis will be assessed separately.

### Interim Data Review Team

The interim data review team will consist of the Sponsor study team, including at least one medical monitor, safety representative, PK representative, biostatistician, and one representative from Novartis, which is partner in the development of AMG 334.

At each interim analysis, this team will review the PK and safety data.

### Early Stopping Guidelines

No early stopping rules are planned

## 7.2 Primary Analysis

**The primary analysis for the study will be performed at the End of the Study milestone described in the protocol Section 3.5.2. All data will be cleaned and a database lock will occur.**

No formal hypothesis testing will be performed; all analyses will be descriptive. PK and safety data will include summaries by body weight cohort and AMG 334 treatment dosage group. **Primary analysis will include safety summaries for ITP only. Safety data will be analyzed by GBS and PK data will be analyzed by CPMS.** The review of the results of this primary analysis will inform on further pediatric studies utilizing AMG 334.

## 7.3 Final Analysis

The final analysis will **utilize the same database as the primary analysis.**

No formal hypothesis testing will be performed; all analyses will be descriptive. PK and safety data will include summaries by body weight cohort and AMG 334 treatment dosage group. **Final analysis will include safety summaries for the entire study and separately for OEP only, as appropriate. Safety data will be analyzed by GBS and PK data will be analyzed by CPMS.**

## 8. Data Screening and Acceptance

### 8.1 General Principles

The objective of the data screening is to assess the quantity, quality, and statistical characteristics of the data relative to the requirements of the planned analyses.

### 8.2 Data Handling and Electronic Transfer of Data

The Amgen Global Study Operations-Data Management (GSO-DM) department will provide all data to be used in the planned analyses. This study will use the RAVE database.

Details of PK, [REDACTED], and external lab data transfer to the database is provided in the corresponding study data transfer plans. See Data Management Plan (DMP) and Data Acquisition Requirements Specification (DARS).

### 8.3 Handling of Missing and Incomplete Data

In general, missing data will not be imputed. However, missing and incomplete dates for AEs and concomitant medications will be handled using the methods described below.

#### Imputation Rules for Partial or Missing Start Dates

	Missing	Imputation	Exception on Adverse Event Start Date
Start date (AE, concomitant medication)	Day	01	Default to Study Day 1 if an adverse event starts the same year and month as Study Day 1 and the flag indicates that the adverse event started on or after the first dose on the Events eCRF
	Day/Month	01JAN	Default to Study Day 1 if an adverse event started the same year as Study Day 1 and the flag indicates that the adverse event started on or after the first dose on the Events eCRF
	Day/Month/Year	No imputation	

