## 5. Definitions

### 5.1 Definition of Terms Included in Study Endpoints

#### Treatment-emergent AE

Events categorized as Adverse Events (AEs) starting on or after first dose of investigational product as determined by “Did event start before first dose of investigational product” equal to “No” or missing on the Events electronic case report form (eCRF) and up to the End of Study date.

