#### **5.4 Study Time Interval**

##### **5.4.1 Study Periods**

The following data will be categorized into treatment periods, if applicable. Any data occurred after EOS date will not be included in the analysis [REDACTED]

Study Phase	Start Time Point	End Time Point
Initial Treatment Phase	Study Day 1	
For Treatment-emergent Adverse Event:
 

• Min (First OEP Dose Date – 1, EOS date) for subjects who received OEP dose;

• EOS Date, for subjects who did not receive any OEP dose

 
For lab, ECG, [REDACTED], Neurological Evaluation and Vital Signs:
 

• Min (First OEP Dose Date, EOS date) for subjects who received OEP dose;

• EOS Date, for subjects who did not receive any OEP dose

 
[REDACTED]

Study Phase	Start Time Point	End Time Point
Optional Extension Phase	For Treatment-emergent Adverse Event: • First OEP Dose Date For [REDACTED] lab, ECG, [REDACTED] Neurological Evaluation and Vital Signs: • First OEP Dose Date + 1	For Treatment-emergent Adverse Event, lab, ECG, [REDACTED] Neurological Evaluation and Vital Signs: • EOS Date
Entire Study	Study day 1	EOS

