### Exposure-adjusted Incidence Rate

The exposure-adjusted incidence rate for a given event in a given period is defined as the number of subjects with at least one reported occurrence of the event in a given period divided by total exposure time of all subjects who are at risk for the event. For subjects with a given event, only the time until the onset of each subject's first event contributes to the exposure time. For subjects without a given event, the exposure time

is the entire duration of the period. This incidence rate will be presented as number of subjects per 100 subject-years.

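### SAP 8.3 does not treat a blank pre-dose flag as SAP 5.1 does, so some treatment-emergent adverse events with partial start dates would be dated before Study Day 1

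*SAP*

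**What the plan says.** Four parts of the SAP bear on this.

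- **SAP 5.1, Treatment-emergent AE.** Status is decided by the eCRF question on whether the event began before the first dose. The answer that qualifies is 'No' "or missing on the Events electronic case report form (eCRF) and up to the End of Study date". A blank flag therefore counts as treatment-emergent.
- **SAP 8.3, Imputation Rules for Partial or Missing Start Dates.** A missing day becomes 01, and a missing day and month become 01JAN. There are two exceptions. With the day missing: "Default to Study Day 1 if an adverse event starts the same year and month as Study Day 1 and the flag indicates" onset at or after the first dose. With day and month missing: "Default to Study Day 1 if an adverse event started the same year as Study Day 1 and the flag indicates" the same. A wholly missing date gets "No imputation".
- **SAP 5.4.1, Study Periods.** "The following data will be categorized into treatment periods, if applicable". The initial treatment phase and the entire-study period both start at Study Day 1. The extension starts thus: "For Treatment-emergent Adverse Event: • First OEP Dose Date". The initial phase ends the day before that dose at the latest, or at "EOS Date, for subjects who did not receive any OEP dose".
- **SAP 5.6.** Subject incidence is defined within a period. For the exposure-adjusted rate, in subjects with the event, "only the time until the onset of each subject's first event contributes to the exposure time".

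Subject incidence of treatment-emergent events is a primary endpoint (SAP 2.1), and the primary analysis summarises safety for the initial phase only (SAP 7.2).

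**The concern.** The same blank flag is resolved in one place and left unresolved in another. SAP 5.1 reads it as on or after first dose. SAP 8.3 asks for a flag that positively indicates this, which a blank does not, so the general 01 or 01JAN rule applies and normally gives a date before Study Day 1. The event is then treatment-emergent by definition but belongs to no analysis period.

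The programmer can leave it out of the period tables, in which case the subject also contributes full event-free time to the exposure-adjusted rate. Or the programmer can keep it, in which case the subject contributes negative time. Neither is intended, and the SAP does not say which applies.

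A second, smaller gap concerns adolescents who enter the extension. Events are allocated between phases by the first extension dose date, but SAP 8.3 never uses that date. When the recorded month or year contains that dose, the earliest compatible date can fall in the initial phase, which is the phase that the primary analysis summarises.

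**Working it through.** The SAP gives no figure to reproduce, so the check applies its date rules literally.

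**Worked example.** Study Day 1 = 14JUN2019; first extension dose at nominal Day 85 = 06SEP2019.

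| Recorded onset | Flag | Imputed date | Period under SAP 5.4.1 |
|---|---|---|---|
| JUN2019 | No | 14JUN2019 | initial phase |
| JUN2019 | blank | 01JUN2019 | none |
| AUG2019 | blank | 01AUG2019 | initial phase |
| SEP2019 (true onset 20SEP) | No | 01SEP2019 | initial phase; truly extension |
| OCT2019 | No | 01OCT2019 | extension |
| 2019 only (true onset 20NOV) | No | 14JUN2019 | initial phase; truly extension |
| 2019 only (true onset 20NOV) | blank | 01JAN2019 | none |
| 2020 only (true onset 20MAR) | blank | 01JAN2020 | extension |

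In the second row, SAP 5.3 gives Study Day = 01JUN − 14JUN = −13, so time to onset is negative.

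**Enumeration.** Inputs from the documents: first extension dose at Day 85, last visit at Day 449 (extension) or Day 169 (no extension), and the SAP 8.3 and 5.4.1 rules. Assumptions not in the documents: Study Day 1 is uniform over the 365 dates of one calendar year (2019), and onset is uniform over follow-up.

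*Blank flag, day missing, month of Study Day 1.* In a month of L days there are L(L+1)/2 pairs of Study Day 1 and later-or-equal onset day. Only the L pairs with Study Day 1 on the 1st survive.

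- All pairs: 7 × 496 + 4 × 465 + 406 = 5,738.
- Surviving pairs: 365.
- In no period: (5,738 − 365)/5,738 = 5,373/5,738 = 93.6%.

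*Blank flag, day and month missing, year of Study Day 1.*

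- Extension subjects: 365 × 366/2 = 66,795 pairs, of which 365 have Study Day 1 on 01JAN. In no period: 66,430/66,795 = 99.5%.
- Subjects without extension: 47,320/47,489 = 99.6%.

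*Blank flag, as a share of all true initial-phase onsets, whatever the month or year.*

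| Missing part | Extension subjects | No extension |
|---|---|---|
| Day | 5,373/30,660 = 17.5% | 5,373/61,685 = 8.7% |
| Day and month | 27,090/30,660 = 88.4% | 47,320/61,685 = 76.7% |

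With day and month missing, a further 39,340/133,225 = 29.5% of true extension onsets also fall in no period.

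*Extension boundary, flag 'No'.* There are 365 × 365 = 133,225 pairs of Study Day 1 and true extension onset.

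- Day missing: 5,394/133,225 = 4.0% move to the initial phase; 96.0% stay.
- Day and month missing: 66,513/133,225 = 49.9% move; 50.1% stay.

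*Blank treated as 'No'.* Events in no period fall to 0 in every scenario. The 4.0% and 49.9% are unchanged.

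**The case against.** The case against has four parts.

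**The loss is not stated.** The visible text of SAP 5.4.1 excludes only data after end of study, and that sentence runs into a redaction. Nothing visible excludes a treatment-emergent event whose imputed date precedes Study Day 1, and a sensible programmer could read the blank flag in 8.3 as 5.1 does. This stands: the defect is an unreconciled rule, not a stated exclusion. It does not remove the need for a sentence, because keeping the event on its imputed date still gives negative time in the exposure-adjusted rate.

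**The cases should be rare.** Onset date is a required attribute and non-serious events are collected only after first dose (Protocol 9.2.1.1). Omissions are queried (Protocol 12.3), and the primary analysis uses cleaned, locked data (SAP 7.2). This also stands. Both the flag and part of the date must be missing, and the documents give no rate for that.

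**Earliest-date imputation is a legitimate choice.** For a safety endpoint it can be called conservative, since it shortens time to first event. That is fair for events that stay inside a period, but not for one dated before all of them.

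**Stronger readings fail.**

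- A reader might infer that every blank-flag partial date is lost. Only those sharing the month or year of Study Day 1 are.
- A reader might infer that imputation always pushes events towards the initial phase. Imputed dates never fall after true onset, but with only the day missing 96.0% of extension onsets keep their phase. Children cannot enter the extension (Protocol 7.2.17), and the blank-flag events land before the initial phase, not in it.
- A reader might put the affected share at 1 − 1/30.4 = 96.7%. That weights Study Day 1 dates equally and ignores that an early Study Day 1 leaves more onset days in the month; 93.6% allows for this.
- With about 12 × 1/3 = 4 subjects on 35 mg at the Cohort 1 minimum, one subject is 25 percentage points. That is the weight of any one subject in four, not a measure of this defect.

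**Conclusion.** The concern holds in a narrow form. SAP 5.1 and SAP 8.3 treat a missing flag differently. Applied literally, SAP 8.3 dates a blank-flag treatment-emergent event before every analysis period when its partial date shares the month or year of Study Day 1, unless Study Day 1 is the 1st (or 01JAN). Under the uniform assumptions this happens to about 93.6% of such events with the day missing and about 99.5% with day and month missing. These are shares of a group whose size the documents do not give and which is probably small, so the effect on the reported incidence cannot be quantified and the point is minor.

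The extension-boundary gap is secondary and confined to adolescents who receive an extension dose: about 4% of extension onsets with the day missing, and about 50% with day and month missing and flag 'No'. An event moved this way remains in the entire-study summaries (SAP 7.3).

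**What to change.** In SAP 8.3, state that both Study Day 1 exceptions apply when the pre-dose flag is 'No' or missing, as in SAP 5.1. This costs one sentence and a small change to the date-imputation program. It removes every partial-date event that falls in no period.

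For adolescents in the extension, the sponsor should state how an event is allocated when its partial date is compatible with both phases. Several conventions are defensible. Allocating by the visit at which the event was first recorded is one, but it can also misclassify and supplies no onset date for the exposure-adjusted rate. Whichever is chosen should be written down before the tables are produced.

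Neither change reaches a wholly missing start date, which SAP 8.3 leaves unimputed. If any remain after querying, the SAP should say in which period they count.

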#### **8.4 Detection of Bias**

Lack of protocol compliance and the potential for biased statistical analyses will be examined by assessing the incidence of important protocol deviations (IPD) in each age group. The clinical study team will identify and document the criteria for IPD.

#### **8.5 Outliers**

All confirmed outlier data will be included in the analyses presented in this SAP unless there is sufficient scientific justification (eg, IPD leading to invalid data) to exclude them. PK concentration data will be evaluated for outliers by visual inspection, and decisions to re-assay individual samples will be made in accordance with standard CPMS evaluation practice. All excluded observations will be detailed by CPMS along with reasons for exclusion, in accordance with standard CPMS practices.

#### **8.6 Distributional Characteristics**

Not applicable for this study.

#### **8.7 Validation of Statistical Analyses**

Programs will be developed and maintained, and output will be verified in accordance with current risk-based quality control procedures.

Tables, Figures and Listings (TFL) will be produced with validated standard macro programs where standard macros can produce the specified outputs.

The production environment for statistical analyses consists of Amgen-supported versions of statistical analysis software; for example, the SAS System version 9.4 or later.

## 9. Statistical Methods of Analysis

### 9.1 General Considerations

Unless otherwise stated, descriptive statistics will be provided for demographic and baseline characteristic by body weight cohort (< 40 kg and  $\geq$  40 kg), treatment dosage (35 mg, 70 mg and 140 mg), and all subjects combined.

Safety summaries during the **entire study, ITP or OEP, as applicable**, will be provided by body weight cohort (< 40 kg and  $\geq$  40 kg), treatment dosage (35 mg, 70 mg and 140 mg), and all subjects combined.

Where appropriate, **safety** summaries **will be provided by** each age group (adolescents and children) separately.

PK data will be summarized by body weight cohort and treatment dosage.

Descriptive statistics on continuous measurements will include **number of subjects (n)**, means, medians, standard deviations (and standard errors for post-baseline data), first and third quartiles, and minimum and maximum, while categorical data will be summarized using frequency counts and percentages. No formal statistical hypothesis testing will be performed.

When data are summarized by visit, the values recorded against the scheduled visits, including any time windows specified in the protocol will be used.

When assessing post-baseline minimum/ maximum increases or decreases over the study (**eg, shift in lab toxicity grade**), all assessments, including unscheduled assessments will be used.

### 9.2 Subject Accountability

The number and percent of subjects randomized, those who received AMG 334, completed ITP, discontinued the ITP (including reasons for discontinuing), entered the OEP, completed OEP, discontinued the OEP (including reasons for discontinuing), completed investigational product and discontinued investigational product (including reasons for discontinuation) will be summarized. Subjects who withdraw early, reason for withdrawal, and timing of the withdrawal will be reviewed.

Key study dates for the first subject enrolled, last subject enrolled, last subject's end of investigational product and last subject's end of study will be presented.

The number and percent of subjects randomized will be tabulated by study site.

The number and percent of subjects for each analysis set will also be summarized.

### **9.3            Important Protocol Deviations**

IPD categories are defined by the study team before the first subject's initial visit and updated during the IPD reviews throughout the study prior to database lock. These definitions of IPD categories, subcategory codes, and descriptions will be used during the course of the study. Eligibility deviations are defined in the protocol.

The final IPD list will be used to produce the Summary of IPDs table and the list of subjects with IPDs. In addition, a separate listing of all inclusion and exclusion deviations will be provided.

Protocol deviations related to COVID-19 controlled measures will be summarized.

### **9.4            Demographic and Baseline Characteristics**

The following demographic and baseline characteristics will be summarized.

Demographics:

- Age (years) at consent (continuous summary statistics)
- Sex (number and percentage of males and females)
- Ethnicity (number and percentage in each ethnicity category)
- Race (number and percentage of subjects in each race, or mixed-race combination). If multiple races have been reported for a subject, the subject will be categorized as multiple race (as well as by combination of races).

Baseline Characteristics:

- Height, weight and BMI (continuous summary statistics)

## 9.5 Efficacy Analyses

[figure not shown]
Not applicable for this study.

## 9.6 Safety Analyses

### 9.6.1 Analyses of Primary Safety Endpoint(s)

Primary and exploratory safety endpoints are summarized in the table below.

**Table 9-1. Safety Endpoint Summary Table**

Endpoint	Primary Summary and Analysis Method
Primary Safety Endpoint  

• Subject incidence of treatment-emergent adverse events (AEs)

• Changes in vital signs, 12-lead electrocardiograms (ECGs), clinical laboratory safety tests, and neurological assessments

	Summary statistics will be provided by body weight cohort and treatment dosage group
Exploratory Safety Endpoint  	

### 9.6.2 Adverse Events

The Medical Dictionary for Regulatory Activities (MedDRA) version 24.1 or later will be used to code all events categorized as adverse events to a system organ class and a preferred term.

The subject incidence and exposure-adjusted subject incidence of all treatment-emergent adverse events, treatment-emergent serious adverse events, device-related treatment-emergent adverse events, treatment-emergent adverse events leading to discontinuation of **investigational product**, and fatal adverse events **will be summarized**.

Treatment-emergent adverse events, treatment-emergent serious adverse events, device-related treatment-emergent adverse events, treatment-emergent adverse events leading to discontinuation of AMG 334, and fatal adverse events will be tabulated by system organ class (SOC) in alphabetical order and preferred term (PT) in descending order of frequency. Summaries of treatment-emergent AEs and treatment-emergent serious adverse events will be tabulated by system organ class, preferred term, and

grade. The severity of each AE will be graded using Common Terminology Criteria for AE (CTCAE) version 4.03 criteria.

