## 2.3 Risk Assessment

Aimovig is currently approved for the preventive treatment of migraine (episodic or chronic types) in adults in over 40 countries. Doses greater than or equal to 70 mg and 140 mg (the highest dose level in either cohort in this study) have been given to three cohorts of adults in a multiple ascending dose (MAD) Phase 1 study and four cohorts of adults in a single ascending dose (SAD) Phase 1 study; a cohort of healthy subjects and a cohort of migraine subjects received three doses of 140 mg SC every four weeks (QM), and one cohort of healthy subjects received a dose of 280 mg (administered on Day 1) followed by 2 doses of 210 mg SC (administered on Days 29 and 57). In Phase 2, a dose ranging study (20120178) tested 7 mg, 21 mg and 70 mg SC QM vs placebo. In Phase 3, the maximum dose of both pivotal Phase 3 studies in adults with chronic migraine (Study 20120295) and episodic migraine (Study 20120296) was 140 mg SC, QM. In Phase 2 and Phase 3, 2417 subjects have been exposed at least 3 months to either 70 mg or 140 mg. The identified risks for AMG 334 are documented in [Appendix A](#) of the currently approved IB ( Version 11.0, 10 February 2020). A limited number of adverse drug reactions (injection site reactions, constipation, muscle spasm, and pruritus) have been identified at low frequencies (< 5%) in clinical trials. In post-marketing settings, hypersensitivity reactions (including rash, angioedema and anaphylactoid reactions) and constipation with serious complications have been reported. Available safety data for the clinical trials with AMG 334 are summarized in Section 7.3 of the AMG 334 IB, Annex 2.

Risk mitigation strategies include the monitoring of vital signs, serial ECGs, and adverse events for all subjects at protocol defined time points.

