##### **10.4.2.2 Treatment-Emergent Adverse Events**

Subject incidence of all treatment-emergent adverse events will be tabulated by system organ class and preferred term according to the medical dictionary for regulatory activities (MedDRA) terminology. Tables of fatal adverse events, serious adverse events, adverse events leading to withdrawal from IP or other protocol-required therapies, and significant treatment emergent adverse events will also be provided. Adverse events resulting in treatment discontinuation will be identified.

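### No planned adverse event table counts the children who had a hypersensitivity reaction, and the protocol's table of significant treatment-emergent events is missing from the SAP

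*SAP*

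**What the plan says.** Protocol 2.3 (Risk Assessment) describes two sets of known harms. From clinical trials: "A limited number of adverse drug reactions (injection site reactions, constipation, muscle spasm, and pruritus) have been identified", at frequencies below 5%. From post-marketing use: "hypersensitivity reactions (including rash, angioedema and anaphylactoid reactions) and constipation with serious complications have been reported". No rate is given for the post-marketing harms.

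SAP 9.6.2 uses MedDRA "to code all events categorized as adverse events to a system organ class and a preferred term". The listed event categories "will be tabulated by system organ class (SOC) in alphabetical order and preferred term (PT) in descending order of frequency", and a further table adds grade for all and for serious treatment-emergent events. The same section promises "The subject incidence and exposure-adjusted subject incidence of all treatment-emergent adverse events, treatment-emergent serious adverse events, device-related treatment-emergent adverse events", together with events leading to discontinuation and fatal events. SAP 9.1 presents safety summaries by weight cohort, by dosage and for all subjects combined, and by age group where appropriate.

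SAP 5.6 defines subject incidence as the number of subjects with at least one occurrence of a given event, each counted once, over the number at risk.

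Protocol 10.4.2.2 lists tables of fatal events, serious events and events leading to withdrawal, and ends "and significant treatment emergent adverse events will also be provided". It does not define 'significant'. SAP 9.6.2 has no such table. SAP 10, which records departures from the protocol's analyses, covers an unplanned interim analysis and the timing of the primary analysis but not this omission.

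**The concern.** Incidence of treatment-emergent adverse events is a primary endpoint, and the study is meant to supply preliminary paediatric safety data for Phase 3. The natural question about hypersensitivity is how many children had any such reaction. The protocol itself presents it as a composite, but the SAP defines no event of that name, so its own subject-incidence definition is never applied to it. Rash in one child and angioedema in another would appear in different rows. A child with both would appear in two.

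If the plan is followed as written, that number is not produced. It would have to be assembled later, with the grouping chosen after the data are known. The protocol's table of significant events would have been the obvious place for it, but the SAP does not carry that table.

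**Working it through.** **1. Do the planned outputs give the number?**

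| SAP 9.6.2 output | Gives subjects with hypersensitivity? |
|---|---|
| Preferred-term rows | No: one row per term |
| System organ class rows | No: they count any event in the class, related or not |
| Grade table | No: same rows, split by grade |
| All, serious, discontinuation, fatal | No: not specific to a harm |
| Device-related | No: SAP 5.1 defines it by the investigator's causality answer about the device, not by a set of terms |

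SAP 9.6.2 contains no adverse event listing from which a reader could rebuild the count.

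**2. Why rows cannot be added.** Take three children: one with rash, one with angioedema, one with both. The rows read 2 and 2. The sum is 4 but the answer is 3. From the rows alone, the number of subjects lies anywhere between the largest row (2) and the sum (4).

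**3. Group sizes.** Cohort 1 (12 to 22 subjects, 1:2) gives 4 and 8, up to about 7 and 15. Cohort 2 (35 to 38 subjects, 1:4) gives 7 and 28, up to about 8 and 30. The all-subjects column has 52 to 60.

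**4. Size of the gap.** The documents give no figure for adverse event detection to reproduce; their only design figure concerns PK precision. I therefore assume a grouped incidence of p = 5%, borrowing the ceiling that Protocol 2.3 gives for the clinical-trial reactions.

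Grouped count: P(X ≥ 3) = 1 − Σ(k = 0 to 2) C(n,k) p^k (1−p)^(n−k).

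- n = 60: 1 − (0.046 + 0.145 + 0.226) = 0.583
- n = 52: 1 − (0.069 + 0.190 + 0.255) = 0.485, taking the sum before rounding

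Largest single row: assume each affected subject has one term, equally likely among m. Results of 400,000 multinomial draws:

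| n | m | P(largest row ≥ 3) | Mean of largest row | As share of the true 5% |
|---|---|---|---|---|
| 52 | 3 | 0.16 | 3.2% | 63% |
| 52 | 6 | 0.06 | 2.6% | 52% |
| 60 | 3 | 0.22 | 3.1% | 62% |
| 60 | 6 | 0.08 | 2.5% | 49% |

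**5. Sensitivity to the rate.** P(grouped count ≥ 3) for n = 52 and n = 60:

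| Assumed rate | n = 52 | n = 60 |
|---|---|---|
| 1% | 0.02 | 0.02 |
| 2% | 0.09 | 0.12 |
| 5% | 0.48 | 0.58 |
| 10% | 0.90 | 0.95 |

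**6. Individual arms, grouped, at 5%.** P(count ≤ 2) is at least 0.99 for n ≤ 8, 0.96 for n = 15, 0.84 for n = 28 and 0.81 for n = 30.

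**The case against.** The strongest reply is that the defined endpoint is delivered. Subject incidence of treatment-emergent events is tabulated, neither document promises a grouped incidence for a named harm, and the study is descriptive. The data are MedDRA-coded anyway, so a grouped count can be produced later; what is lost is pre-specification, not data. All of that stands, and it limits the point to a reporting improvement.

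Other readings go further than the documents allow:

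- **A reader might infer that tabulation by preferred term is what produces counts of 0 to 2.** Step 6 shows otherwise: at 5% a grouped harm would usually show 0 to 2 in every arm. Small arms are the main cause.
- **A reader might assume rates of 15 to 20%, which make the contrast striking in the 140 mg arm.** At 15% with n = 28 and 4 to 6 terms it is 0.81 against 0.18 to 0.31. Nothing in the documents supports such rates. At 5% the grouped count in 28 subjects reaches 3 with probability only 0.16.
- **A reader might place injection site reactions on the same footing.** Protocol 2.3 lists component manifestations for hypersensitivity only. That injection site reactions code to several terms is an assumption, and the device-related category may capture some of them.

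The calculation has a limit too. It gives each affected subject one term, so it measures the shortfall of the largest row and not double counting. No document tells the reader to rely on the largest row. Finally, the exploratory row of SAP Table 9-1 is blank and may be redacted, so related content there cannot be excluded; SAP 9.6.2 itself is legible.

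**Conclusion.** The point holds as a cheap improvement. Two parts rest on the text. No visible planned output gives a de-duplicated count of subjects with hypersensitivity, and the protocol's table of significant treatment-emergent events has been dropped without being recorded in SAP 10. The first part takes it that the manifestations named in Protocol 2.3 code to separate preferred terms.

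The size is illustrative. It depends on an assumed 5% incidence, an even split over 3 to 6 terms and one term per subject. On those assumptions the gain lies in the all-subjects column, where the largest row shows about half to two-thirds of the true rate. At 1 to 2% a grouped count of 3 would be uncommon even there. The documents do not support a claim that grouping would yield a usable estimate within each arm, or that the primary safety endpoint goes unreported.

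**What to change.** Add to SAP 9.6.2 one table of subject incidence and exposure-adjusted incidence, using the definitions already in SAP 5.6, for a fixed MedDRA grouping of hypersensitivity that includes angioedema and anaphylactic-type terms. Name the grouping and the dictionary version in the SAP. Add a group for injection site reactions if these prove to code to more than one preferred term.

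Count each subject once per group and show the preferred-term breakdown beneath. Present the table by weight cohort, by dose and for all subjects combined. Designate it as the significant-event table of Protocol 10.4.2.2; if it is not adopted, record in SAP 10 that the promised table will not be produced. Separate groups for muscle spasm and pruritus are not needed, since no splitting is shown for them.

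The cost is one SAP paragraph and one output from data already coded, with no new data collection. The drawback is that a broad grouping will include some unrelated events, which is why the term breakdown should sit beneath each group total.
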